1. Screening evaluations for patients on pain medication that is not permitted should be scheduled so as to allow for a minimum washout of 7 days prior to the start of the Pain Observation period. Patients who are not taking pain medication and do not require washout can be scheduled for Screening evaluations at any time during the period with the understanding that it may take several days before laboratory results are available.
2. All patients are required to complete the Pain Observation period from Day -14 to Day -1. During the Pain Observation Period, on Day -7 to -5, a phone contact to the patient will be conducted to review diary and dosing compliance and provide re-training as necessary. The Day 1 clinic visit will be scheduled during this call. A patient may be randomized after 10-14 days in the Pain Observation period if all eligibility requirements have been met. An algorithm comprised of several aspects of the diary data will determine final eligibility prior to randomization.
3. C-SSRS Screening version used for Screening. Subsequent visits will use the Since Last Visit version.
4. Vital signs include temperature, respiration rate, pulse, and blood pressure while patient is sitting after a minimum 5-minute rest. Standing pulse and blood pressure to be obtained following sitting vital signs.
5. A comprehensive physical examination will be performed at Screening; subsequent physical examinations will be directed exams to assess changes from the prior visit or new concerns.
6. Skin breaches and wounds will be examined and the following parameters recorded: location, size, depth, and evidence of erythema, edema, warmth, odor, or drainage.
7. 12-lead ECG after the patient has been resting in the supine position. On Day 1, an additional 12-lead ECG will be obtained 1 hour (+/- 10 minutes) post-dose.
8. Chemistry will be collected in a fasting state (8 to 10 hours fasting).
9. A urine pregnancy test is required at Screening and Day 1 (prior to randomization) for females of child-bearing potential, and must be negative for treatment to proceed.
10. Only for females less than 60 years of age with less than 2 years since last period.
11. Only required if any recent exposure within past 14 days prior to screening to COVID-19 and/or symptoms of COVID-19 along with reason to suspect COVID-19.
12. Urine drug screen is required at Screening and Week 8, and may be performed at any other visit at the discretion of the Investigator.

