## **7.0 INVESTIGATIONAL PLAN**

### **7.1 Overall Study Design and Plan Description**

This is a randomized, double-blind, 2-arm, parallel group study of up to 274 evaluable patients designed to evaluate the safety and efficacy of ricolinostat for painful DPN.

After signing the ICF and agreeing to participate, initial eligibility assessments will be completed during a Screening visit scheduled between 45 and 14 days prior to planned randomization. Patients may continue one permitted medication for painful DPN if they have been taking it for at least 3 months prior to Screening, provided that the regimen and dose have been stable for at least 3 months prior to Screening and are expected to remain unchanged for the duration of the study. If any pain medication is stopped during the Screening period, then prior to proceeding to the Pain Observation Period:

1. The Investigator must document that there has not been a 'rebound flare,' or that if such a flare has occurred, it has resolved.
2. The Investigator must document that a steady state pain baseline is present.
3. A minimum period of time equal to at least 5 half-lives of the drug in question must pass.

Prior to randomization, patients will participate in a baseline Pain Observation period from Day -14 to Day -1, during which the NRS (average and worst pain) will be recorded daily using an electronic daily diary that will be completed by patients to allow patients to familiarize themselves with the pain rating procedures along with initiation of daily placebo dosing. During the Pain Observation period and thereafter during the study, patients will be allowed to use acetaminophen as rescue pain medication at a maximum dose of 500 mg at 6-hour intervals up to 4 times in any given 24-hour period. Patients will record the pain assessments and any rescue medication use. A follow-up phone contact will be conducted at Day -7 to Day -5 to review diary and dosing compliance.

At the end of the Pain Observation period, patients whose diary compliance, overall level of pain, and pain variability, along with placebo dosing meet entry criteria, will be randomized in a 1:1 ratio to receive either ricolinostat or placebo.

Pre-Treatment assessments will be completed as outlined in [Table 1](#). The first dose of study drug will be given in the clinic and a 12-lead ECG will be performed 1-hour post-dose.

[figure not shown]

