### 8.4.1 Concomitant Pain Medications and Therapies

Patients who have been on a stable regimen of an allowed pain medication (see Section 8.4.2 below) for at least 3 months prior to Screening and who have ongoing diabetic neuropathic pain that meets entry criteria may continue those medications during the study provided there is no plan to change the regimen during the study. Any pain medication that a patient has been previously taking on a regular basis but no longer takes must have been discontinued for at least one month prior to starting the Pain Observation period. Pain medications taken on an occasional or as needed basis (3 or less days in most weeks) must have been discontinued for at least 7 days prior to starting the Pain Observation period.

Patients who have continued to experience pain while using non-drug therapies for pain (eg, acupuncture, mindfulness therapy, etc) that have been ongoing for at least 3 months may continue these during the study, provided the type and intensity of such treatment remains stable during the course of the study. The following medications/devices are not permitted during the study:

- Non-steroidal anti-inflammatory drugs (NSAIDs including Advil and Motrin [ibuprofen], Aleve [naproxen, Bayer and Ecotrin [aspirin], etc).
- Opioid medications including, but not limited to, OxyContin (oxycodone), Percocet (oxycodone and acetaminophen), Vicodan (hydrocodone), Percodan (oxycodone and aspirin), Tylox (oxycodone and acetaminophen capsules), Demerol (meperidine), Ultram (tramadol), Nucynta (tapentadol), etc.
- Cannabinoids, including CBD.
- Topical preparations containing capsaicin, NSAIDs, or numbing agents (eg, lidocaine).
- Implanted medical devices (eg, spinal cord stimulator, intrathecal pump, or peripheral nerve stimulator).

No patient may participate in the study if he/she has enrolled or previously (prior 30 days before initiation of the Screening period) participated in a study of an investigational drug, biologic, or medical device. Participation in a concomitant observational study where no treatment intervention is planned is allowed, provided the demands of such a study do not, in the opinion of the Investigator, overly burden the patient or put treatment study objectives at risk.

Patients will be queried about pain medications and therapies during each visit to determine if any of the prohibited items are being used.

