## **9.0 STUDY VISITS AND PROCEDURES**

### **9.1 Schedule of Study Procedures**

The tabular schedule of assessments is provided in [Table 1](#). The study is comprised of a Screening, Washout, Pain Observation, Treatment, Safety Extension, and Follow-up period as outlined in the sections below.

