### **9.2 Screening and Washout Period (Day -45 to Day -14)**

The timing of Screening evaluations will depend in part on whether the patient is using pain medications other than those permitted and described in Section [8.4.2](#). Patients on pain medication that is not permitted and taken on a regular basis should be scheduled so as to allow for a minimum of at least one month (30 days) washout prior to the start of the Pain Observation period. Patients on pain medication that is not permitted and taken on an occasional or as needed basis (3 or less days in most weeks) should be scheduled so as to allow for a minimum washout of 7 days prior to the start of the Pain Observation period. Patients who are not taking pain medication and do not require washout can be scheduled for Screening evaluations at any time during the period with the understanding that it may take several days before laboratory results are available. All Screening and Washout procedures must be completed by Day -14 to allow for a 14-day Pain Observation period prior to randomization.

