**Exhibit 3. Schedule of events, continued**

	Pain Observation Period 														
	Screening		Placebo (Single-Blind) Lead-In		Double-Blind, Placebo-Controlled Treatment Period				Open Label Safety Extension				Follow-up Period		
	Screening Evaluation 	Washout	Training Visit	Training Follow-up	Pre-Treatment Baseline	Week 1	Week 2	Week 4	Week 8	Week 12	Week 14	Week 18	Week 24	Week 26	Week 28
Day	-45 to -14		-14 to -7	-7 to -5	1	5 to 9	12 to 16	26 to 30	54 to 58	82 to 86	96 to 100	124 to 128	166 to 170	180 to 184	194 to 198
Review prohibited medications and rescue medication guidelines			x												
Phone contact and diary review				x 											

Note: If a patient is discontinued early from the study for any reason, the investigator should make every effort to ensure that the final assessments at Week 24 are completed as outlined in the schedule of events. The reason for discontinuation will be recorded in the patient’s record and the study database.

1. Screening evaluations for patients on pain medication that is not permitted should be scheduled so as to allow for a minimum washout of 7 days prior to the start of the Pain Observation period. Patients who are not taking pain medication and do not require washout can be scheduled for Screening evaluations at any time during the period with the understanding that it may take several days before laboratory results are available.
2. All patients are required to complete the Pain Observation period from Day -14 to Day -1. During the Pain Observation Period, on Day -7 to -5, a phone contact to the patient will be conducted to review diary and dosing compliance and provide re-training as necessary. The Day 1 clinic visit will be scheduled during this call. A patient may be randomized after 10-14 days in the Pain Observation period if all eligibility requirements have been met. An algorithm comprised of several aspects of the diary data will determine final eligibility prior to randomization.
3. C-SSRS Screening version used for Screening. Subsequent visits will use the Since Last Visit version.
4. Vital signs include temperature, respiration rate, pulse, and blood pressure while patient is sitting after a minimum 5-minute rest. Standing pulse and blood pressure to be obtained following sitting vital signs.

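### Table 1 footnote 1 (and its SAP copy) allows a 7-day washout for every non-permitted pain drug, while Sections 9.2 and 8.4.1 require a month for regular use

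*Protocol*

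**What the plan says.** **The schedule.** Protocol Table 1, footnote 1, states that Screening evaluations for "patients on pain medication that is not permitted should be scheduled so as to allow for a minimum washout of 7 days" before the Pain Observation period. SAP Exhibit 3, footnote 1, repeats the rule: evaluations "should be scheduled so as to allow for a minimum washout of 7 days prior to the start of the Pain Observation period". Neither footnote mentions how often the drug was taken.

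**The text sections.** Protocol Section 9.2 divides the rule by frequency of use. For non-permitted medication taken regularly it asks for a "minimum of at least one month (30 days) washout prior to the start of the Pain Observation period". The 7-day period is kept for patients whose non-permitted drug is "taken on an occasional or as needed basis (3 or less days in most weeks) should be scheduled" with that shorter minimum. Section 8.4.1 makes the same division in mandatory terms: a drug formerly taken regularly "must have been discontinued for at least one month prior to starting the Pain Observation period", while one taken occasionally or as needed "must have been discontinued for at least 7 days prior to starting the Pain Observation period".

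**How they relate.** Section 9.1 says "The tabular schedule of assessments is provided in" Table 1, and in the same paragraph refers the reader to the sections that follow. It does not rank them. Section 7.1 adds conditions for any pain drug stopped during Screening. The investigator must document that there was no rebound flare or that it has resolved, and that pain is at steady state. In addition, "A minimum period of time equal to at least 5 half-lives of the drug in question must pass".

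**The concern.** The length of the washout is an operative instruction, and the current text gives two different lengths for the same patient. A 30-day washout in a regular user satisfies every text. A 7-day washout in that user satisfies the footnotes and breaches 9.2 and 8.4.1. The schedule table is the page a coordinator is likely to book visits from, and the shorter rule is much the easier one to schedule.

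Two things are at stake. First, with about 50 sites, the washout actually applied to regular users may depend on which page a site consulted. None of the numbered inclusion or exclusion criteria states the one-month rule, so checking those criteria alone would not expose a short washout. Second, the primary endpoint is change from a diary baseline, and the plan itself treats recent withdrawal as a threat to that baseline through the flare and steady-state conditions of 7.1. A regular user who stopped only a week before Pain Observation may supply a noisier baseline.

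**Working it through.** The plan derives no figure here, so the check is a comparison of texts followed by day counts.

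**Inputs**
- Footnote minimum, any non-permitted pain drug: 7 days (Protocol Table 1; SAP Exhibit 3).
- Regular use: one month (8.4.1), given as 30 days in 9.2. Occasional use: 7 days (both sections).
- Screening window opens on Day -45 (9.2).
- Pain Observation lasts 10 to 14 days before randomization (9.3.2), so it starts between Day -14 and Day -10.
- First baseline diary day: Day -7 in Protocol 10.3.3. SAP 6.1.3 instead averages the 5 to 9 days before randomization, so its first day lies between Day -9 and Day -5.

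**Step 1. Latest permitted last dose for a regular user** (start of Pain Observation minus washout)

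| Pain Observation starts | 7-day rule | 30-day rule | Gap |
|---|---|---|---|
| Day -14 | -14 - 7 = Day -21 | -14 - 30 = Day -44 | 44 - 21 = 23 days |
| Day -10 | -10 - 7 = Day -17 | -10 - 30 = Day -40 | 40 - 17 = 23 days |

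The gap is 30 - 7 = 23 days whatever the start day.

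**Step 2. Time from last dose to first baseline rating**
- Protocol baseline (Day -7). 7-day rule: 21 - 7 = 14 and 17 - 7 = 10, so 10 to 14 days. 30-day rule: 44 - 7 = 37 and 40 - 7 = 33, so 33 to 37 days.
- SAP baseline (Day -9 to Day -5). 7-day rule: from 17 - 9 = 8 to 21 - 5 = 16 days. 30-day rule: from 40 - 9 = 31 to 44 - 5 = 39 days.

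SAP Section 1 makes the SAP govern where the planned analyses differ, so the second set is the one relevant to the analysis. The 23-day difference is the same in both.

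**Step 3. Screening days open to a regular user**, assuming the drug is stopped on the Screening day
- Day -14 start: footnote 45 - 21 + 1 = 25 days; Section 9.2 45 - 44 + 1 = 2 days.
- Day -10 start, Section 9.2: 45 - 40 + 1 = 6 days.

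**Step 4. Does another rule close the gap?** Five half-lives reach 30 days only for a drug with a half-life of at least 30 / 5 = 6 days, so 7.1 does not in general restore the month. The SAP's precedence clause concerns planned analyses, and the SAP copy carries the 7-day text in any case.

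**The case against.** The strongest reply is that the conflict is slight. The footnote is advice on booking a visit and states only a minimum, while 8.4.1 is a mandatory rule in the medication section and 9.2 repeats it. A careful site would read the footnote as an abbreviation and apply the month. Even a site that did not would meet 7.1: a patient whose pain is still shifting after a drug was stopped during Screening may not enter Pain Observation. Exclusions 8, 10 and 13 also remove heavier opioid use, recent cannabis use and much capsaicin use. Pain medication taken in the 30 days before Screening is recorded (8.4), so a short washout can be seen by monitors.

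Most of this stands, and it limits the harm. It does not remove the contradiction. Steady-state documentation rests on investigator judgement and is a different requirement from a fixed month off the drug. Regular use of NSAIDs, lower-level opioid use and other topical agents remain within reach of the footnote.

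Three stronger readings are tempting and are not supported:
- *Bias or lost power.* A reader might infer that the treatment comparison is distorted. Randomization is 1:1 and blocked by site, so a site's washout habit falls on both arms. The documents give no figure for pain drift after withdrawal from which a power effect could be derived.
- *A third conflicting rule.* The five half-lives in 7.1 are a compatible further minimum.
- *A second contradiction in 8.4.2.* That section lets patients above a dose cap reduce to it, with 7 days at the new dose. This is an express permission and works as an exception to the stability conditions around it. The only real tension is with the sentence in 7.1 that asks for three months at a stable dose before Pain Observation, and a cross-reference would settle that. Requiring the flare and steady-state notes after a dose cut would be a new demand, not a correction.

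**Conclusion.** The point holds as an internal contradiction in current version 5.0 text. Both footnotes are wrong as written for regular users of non-permitted pain drugs: they permit a washout 23 days shorter than 9.2 and 8.4.1 require. That gap follows from the documents alone, taking one month as the 30 days stated in 9.2.

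The consequence is modest: inconsistent application of the washout rule across sites, and possibly more noise in baseline pain among regular users admitted early. The documents show neither how many such patients there would be nor how far their ratings would move, so that part cannot be sized. The 7.1 conditions, the Pain Observation period, the variability bound in inclusion criterion 7 and baseline pain as a model covariate all reduce it. The intended design, a month for regular use and a week for occasional use, is clear and not in dispute. No sample-size figure, test or estimand changes. The correction is still worth making, because two sections contradict a number that sites act on and the change is small.

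**What to change.** Rewrite footnote 1 in Protocol Table 1 and in SAP Exhibit 3 to match 9.2 and 8.4.1: at least 30 days before Pain Observation for non-permitted pain drugs taken regularly, and at least 7 days for those taken occasionally or as needed (no more than three days in most weeks). Add that a drug stopped during Screening must also have been off for five half-lives under 7.1, with the longer period governing. Send sites a short clarification. Optionally, add to the three-month stability sentence in 7.1 a cross-reference to the dose reduction allowed in 8.4.2.

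The drafting cost is two footnotes and a site notice. The change adds nothing for sites already following 9.2. Sites that have applied 7 days to regular users would have to wait up to 23 more days, in a tight window: on the stop-at-Screening assumption, 2 possible Screening days for a Day -14 start and 6 for a Day -10 start. Sections 9.2 and 8.4.1 already impose that constraint. The correction makes it visible but does not relieve it.

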#### **4.0 ETHICAL CONSIDERATIONS**

##### **4.1 Independent Review Board**

In accordance with the US Code of Federal Regulations (CFR) 21 CFR 56, the protocol, ICF, any additional information for patients, and patient recruitment materials will be submitted to a properly constituted Institutional Review Board (IRB) prior to commencing the study.

Verification of the IRB's review and approval of the protocol, ICF, and other materials will be required before investigational product is shipped to the study sites and study enrollment begins.

All subsequent protocol amendments or changes to the ICF, information for patients, and/or recruitment materials will be submitted to the IRB for review and approval prior to implementation. The IRB will be informed of any new information that becomes available during the study that could impact patient health and safety, including the occurrence of Suspected Unexpected Serious Adverse Reactions (SUSARs).

Periodic and final progress reports will be submitted to the IRB at appropriate intervals not to exceed 1 year.

##### **4.2 Ethical Conduct of the Study**

The study procedures outlined in this protocol will be conducted in accordance with the CFR governing Protection of Human Patients (21 CFR 50), Financial Disclosure by Clinical Investigators (21 CFR 54), Institutional Review Boards (21 CFR 56), Investigational New Drug Application (21 CFR 312), and with the International Conference on Harmonisation Good Clinical Practice (ICH E6 GCP) guidelines, as appropriate. As such, this study will be conducted in accordance with the ethical principles that have their origin in the Declaration of Helsinki.

##### **4.3 Patient Information and Consent**

Each study patient, upon deciding to participate, will sign the IRB-approved ICF before any study-related procedures are performed. The Investigator will ensure that each patient being considered for inclusion in this study is given a full explanation of the procedures and expectations for study participation. Study personnel will adhere to the requirements of 21 CFR 50 when obtaining consent from any potential study candidate, including explaining the rationale for and the details of the study, the risks and benefits of alternative treatments, and the extent of involvement. Once the essential information has been provided to the patient and fully explained by the Investigator (or a qualified designee) and it is felt the patient understands the implications and risks of participating in the study, the IRB-approved ICF will be signed and dated.

The patient will be given a copy of the signed consent, and the original will be maintained with the patient's records.

## **5.0 INTRODUCTION**

### **5.1 Diabetic Neuropathic Pain**

According to recent estimates, more than 400 million people worldwide and more than 30 million in the United States suffer from diabetes mellitus, while an additional 80 million people in the United States are prediabetic and at increased risk for progression to frank diabetes within 5 years (World Health Organization, 2016; Centers for Disease Control and Prevention, 2014). This constitutes a major health problem, as diabetes is associated with a number of complications that lead to significant morbidity and disability. Among the most common complications are diabetic neuropathies, which occur in up to 50% of patients and are characterized by loss of sensation, paresthesias, and, in approximately 10% to 20% of patients, pain (Pop-Busui R et al, 2017; Barrett, 2007; Veves, 2008). Patients with diabetic peripheral neuropathy (DPN) and diabetic neuropathic pain experience functional impairments as well as reduced quality of life, with negative effects on physical, emotional, social functioning, and sleep (Davies, 2006; Pop-Busui R et al, 2017).

### **5.2 Medical Need**

Pharmacologic treatments for diabetic neuropathy have been shown to be efficacious for diabetic neuropathic pain, and not for other aspects of diabetic neuropathy. Multiple drugs including tricyclic antidepressants (eg, amitriptyline), selective serotonin-norepinephrine reuptake inhibitors (SSNRIs) (eg, duloxetine), anticonvulsants (eg, gabapentin, pregabalin), and opiates (eg, oxycodone, tramadol) are used, but only pregabalin (Lyrica®), duloxetine (Cymbalta®), and the opioid tapentadol-ER (Nucynta) are approved by the US Food and Drug Administration (FDA) for the treatment of diabetic neuropathic pain. Unfortunately, many patients' symptoms fail to respond to these drugs, and among responders, few patients experience complete symptom control and remission of pain. Additionally, the available medications are associated with unwanted effects, and many patients tolerate them poorly. There thus remains a large, unmet medical need for new treatments that are efficacious and well-tolerated in patients with diabetic neuropathic pain, as well as more broadly for the treatment of diabetic neuropathy.

